5.3 Pharmacodynamic Assessments

5.3.1 Leg MRI/MRS (Cohorts 1 and 2)

The following leg muscle MRI/MRS parameters will be measured at Baseline and Weeks 12, 24, 36 and 48 during the first 48 weeks and then 6 monthly during the extension phase:

- MRS method
 - Fat Fraction in the Vastus Lateralis (MRS_FF_VL)
 - Fat Fraction in the Soleus (MRS_FF_SOL)

- Water Transverse Relaxation Time (1H2O-T2) in the Vastus Lateralis (MRS _T2_VL)
- Water Transverse Relaxation Time (1H2O-T2) in the Soleus (MRS _T2_SOL)
- 8 point Dixon method
 - Fat Fraction in the Vastus Lateralis (DIX_FF_VL)
 - Fat Fraction in the Soleus (DIX_FF_SOL)
 - Fat Fraction in the Biceps Femoris (DIX_FF_BFLH)
- MRI method
 - Proton Transverse Relaxation Time (T2) in the Vastus Lateralis (MRI_T2_VL)
 - Proton Transverse Relaxation Time (T2) in the Soleus (MRI_T2_SOL)
 - Proton Transverse Relaxation Time (T2) in the Biceps Femoris (MRI_T2_BFLH)

The MRS parameters from the Vastus Lateralis and Soleus are considered the primary MRI/MRS parameters for the study.

The fat fractions are reported as percentages, whilst T2 parameters are reported in ms.

Imputation will not be used for any missing data.

If a subject withdraws from the study prematurely they will also be assessed at the termination visit if not performed in the last 6 weeks.

Changes from baseline will be calculated.

The following velocities of change (change per month) will also be calculated for the MRS fat fraction measurements:

- Baseline to Week 12
- Week 12 to Week 24
- Week 24 to Week 36
- Week 36 to Week 48

And

- Baseline to Week 24
- Week 24 to Week 48

... and so forth when reporting the extension phase data

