Section 5 provides details of where efficacy data is imputed if the reason given for not performing or completing an assessment is related to the subject's medical condition (e.g. if a subject is physically unable to do the 6MWD then their distance will be imputed as 0). For such efficacy endpoints the number of imputed values will also be tabulated along with other descriptive statistics in summary tables.

Listings will present cohort as a sub-header. Unless otherwise specified, tabulations will present data for each cohort separately as well as all subjects.

In by-time summary tables the baseline will be summarized using all available data, but also for each visit using only the baseline data from subjects with available data at the visit; hence the mean change from baseline will equal the mean visit value – mean baseline value.

All data will be listed and will present study days in addition to dates. Dates will be presented in DDMMYY format (e.g. 28Jul2017).

Listings will be sorted by cohort (used as sub-header), subject and, where appropriate, time.

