9.1.1 Methods for Handling Dropouts and Missing Data

Imputation details concerning missing efficacy data where a subject has attended the relevant visit are discussed in **Section 5**. Where missing data is due to a missed visit values will not be imputed.

The imputation approaches for handling partial or missing start and/or end dates of AEs and concomitant medications are summarized in **Appendix 2**. Partial and missing AE or concomitant medication dates will be imputed with conservatism. Unless an AE is proven to occur prior to the first dose of the study drug, it will be considered to be a treatment-emergent adverse event (TEAE). Similarly, a medication with a missing stop date will be considered as concomitant medication unless there is obvious evidence that the stop date is prior to the first date of IMP treatment. If the day, or month and day, of the start date are not obviously before the date of first IMP treatment, then the start date will be imputed as the first day of the available month and or year, or the start date of IMP, whichever is later.

The imputed dates will be used to assess whether AEs should be considered to be treatment emergent, medications should be included in the safety summaries as prior and/or concomitant, and for the calculation of AE durations; however, the original partial/missing dates will be included in data listings.

Partial dates for age at diagnosis will also have the missing information imputed for the purposes of calculating the duration since diagnosis. The earliest date consistent with the information provided will be used.

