9.7 Pharmacodynamics Analyses

9.7.1 Leg MRI/MRS (Cohorts 1 and 2)

All analyses will be performed using the Leg MRI/MRS population.

Tabulations will be over all subjects and will not provide separate information for the different cohorts.

Absolute values and changes from baseline will be summarized by visit for each of the 10 parameters. The 95% confidence interval will also be included for the mean changes from baseline.

The MRS fat fractions for the Vastus Lateralis and Soleus will be summarized by visit using a shift table from baseline. Marginal totals will be included. The categories used will be < 10%, ≥10% and < 20%, ≥ 20% and < 30%, ≥ 30% and < 40%, ≥40% and < 50%, ≥50% and < 60%, ≥60%.

Vastus Lateralis and Soleus MRS fat fraction and T2 parameters

The following outputs will only be presented for the Vastus Lateralis and Soleus MRS fat fraction and T2 parameters.

The velocities of change will be summarized using descriptive statistics. Velocities of change will also be analyzed using the methods described in [Section 9.6.1](#).

Individual subject data will be plotted against age as individual line plots (spaghetti plots) for each parameter.

Box and whisker plots will display the Baseline, Week 12, Week 24, Week 36 and Week 48 data.

Mean changes from baseline, with associated 95% confidence intervals, will be plotted against visit. As visits in the extension phase will be included the plot will also include the n contributing to the visit.

Week 12, 24, 36 and 48 changes from baseline will also be plotted against age on Day 1 and baseline, using different symbols to identify the Week. The Pearson correlation coefficient (for each week) will be footnoted on the plots.

The changes from baseline for parameters will be plotted against one another for Weeks 12, 24, 36 and 48 data. The week will be identifiable using different symbols. The Pearson correlation coefficients (for each week) will also be presented in the footnote of the plots.

The MRS fat fractions will be plotted against the corresponding MRI fat fractions and the MRS T2 values will be plotted against the corresponding MRI T2 values for the Vastus Lateralis and Soleus muscles. Absolute values will be plotted with different symbols used for each visit. The plot will be repeated for changes from baseline.

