9.7.3 Fibre Regeneration (via Biopsy) (Cohorts 1 and 2)

All analyses will be performed on the Biopsy population.

Tabulations will be over all subjects and will not provide separate information for the different cohorts.

Imputation will not be used for missing data with summaries and plots, and so subjects with missing baseline or Week 24/48 data will be excluded from presentations for the relevant time-point and change from baseline presentations. However, mixed effect models will be used to make comparisons to baseline; these analyses will use all available data and adjusts the results for missing data under the assumption of missing at random.

Summary tables will acknowledge the number of subjects who have their biopsy performed at Week 24 and Week 48 (e.g. if a subject isn't supposed to have a Week 24 measurement it will not be counted as missing).

The total number of fibres assessed with each assay will be summarized using descriptive statistics (n, median, Q1, Q3, minimum and maximum) by visit. These variables won't be included in any other analyses.

The percentage of fibres (%fibre) with 0, 1, 2 and 3 MHCd/Utrphin intensity will be excluded from analyses unless specifically mentioned.

For each assay (Myosin and Utrophin) the number of subjects contributing 1 or 2 samples worth of data will be tabulated for each visit for each of the two groups (Week 24 and Week 48). Where there is 1 sample with data the number of subjects with 1, 2 and 3 sections will be tabulated and where there are 2 samples with data the number of subjects with 2, 3, 4, 5 and 6 sections will be tabulated.

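### For the primary leg MRS parameters, the Week 36 and Week 48 changes from baseline have a stated 95% CI only as observed-case means, and the planned mixed model neither lists those contrasts nor fully corrects for selective loss of scans

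*SAP*

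**What the plan says.** Change from baseline to Weeks 12, 24, 36 and 48 in leg MRI is the first primary endpoint (SAP 4.1). Among its ten parameters, SAP 5.3.1 singles out four: "The MRS parameters from the Vastus Lateralis and Soleus are considered the primary MRI/MRS parameters for the study".

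The by-visit analysis is in SAP 9.7.1: "Absolute values and changes from baseline will be summarized by visit for each of the 10 parameters", and "The 95% confidence interval will also be included for the mean changes from baseline". SAP 5.3.1 adds: "Imputation will not be used for any missing data". The general rule in SAP 9.1.1 agrees: "Where missing data is due to a missed visit values will not be imputed". Under SAP 9.1 the baseline in these tables is also summarized "for each visit using only the baseline data from subjects with available data at the visit", so each mean change belongs to the boys scanned at that visit.

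SAP 9.7.1 has a second analysis of the vastus lateralis and soleus MRS parameters: "Velocities of change will also be analyzed using the methods described in" SAP 9.6.1. That section fits a mixed model to the absolute values at all visits, with visit fixed and subject random. It asks for velocities over 12-week and 24-week steps, and differences between velocities, each with a 95% CI.

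For the secondary biopsy endpoint, SAP 9.7.3 uses mixed models to estimate change from baseline and says that "these analyses will use all available data and adjusts the results for missing data under the assumption of missing at random". Neither 9.7.1 nor 9.6.1 makes such a statement.

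**The concern.** An observed-case mean at Week 48 describes boys who still have a Week 48 scan. It equals the mean change in all treated boys only if boys without a scan would have changed by the same amount on average. There is no control arm in which a similar loss could offset the bias, so any bias passes straight into the absolute Week 48 change. If boys who progress faster are more likely to leave, the fat-fraction rise looks smaller than it is, which favours the drug.

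The SAP plans a model-based change from baseline under missing at random for a secondary endpoint, but not for the primary one. The mixed model it does plan for leg MRS is pointed at velocities, so the mean-change table and plot remain observed-case.

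**Working it through.** **No plan figure to reproduce.** The sample size is not based on power (SAP 3.1), and neither document gives a leg MRI effect size, SD or dropout rate. All numerical inputs below are assumptions.

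**Step 1: bias of the observed-case mean.** Let d be the share of boys without a Week 48 scan, L their mean change and S the mean change in those scanned. The full-population mean is (1 − d)S + dL and the table reports S, so

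bias = S − [(1 − d)S + dL] = −d(L − S).

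| L − S (points) | d = 5% | d = 10% | d = 20% |
|---|---|---|---|
| −5 | +0.25 | +0.50 | +1.00 |
| 0 | 0 | 0 | 0 |
| +5 | −0.25 | −0.50 | −1.00 |
| +10 | −0.50 | −1.00 | −2.00 |

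The sign depends wholly on whether leavers progress faster or slower than stayers.

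**Step 2: what the planned velocities give.** Write V(24−B) = (Week 24 − Baseline)/6 and V(48−24) = (Week 48 − Week 24)/6, as in SAP 9.6.1. Then

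Week 48 − Baseline = 6 × V(24−B) + 6 × V(48−24).

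The point estimate is therefore recoverable. The interval does not follow from the two velocity intervals alone, because Var(sum) = Var₁ + Var₂ + 2Cov. SAP 9.6.1 also lists the difference of these two velocities with a CI, so a determined reader could approximate it through Var(sum) = 2Var₁ + 2Var₂ − Var(difference). The SAP does not ask for this. Week 36 − Baseline = 6 × V(24−B) + 3 × V(36−24), and the difference of those two velocities is not listed.

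**Step 3: how far the planned model corrects the bias.** A simulation of 100,000 boys with scans at 0, 3, 6, 9 and 12 months assumed:
- baseline fat fraction with mean 20% and SD 12;
- a mean rise of 5 points a year, with slope SD 4 or 6 between boys and residual SD 2;
- 10% or 20% of boys lost by Week 48, with losses from the Week 24 visit on;
- a risk of loss that was unrelated to progression, or rose by a factor e per SD of either the observed rise or the true slope.

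Bias in the Week 48 change, in points:

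| Loss depends on | Slope SD | Loss | Observed-case | Random intercept (SAP 9.6.1) | Unstructured |
|---|---|---|---|---|---|
| nothing | 4 or 6 | 10–20% | −0.02 to 0.00 | −0.01 to 0.00 | −0.01 to 0.00 |
| observed rise | 4 | 10% | −0.34 | −0.16 | 0.00 |
| observed rise | 4 | 20% | −0.73 | −0.35 | 0.01 |
| observed rise | 6 | 10% | −0.54 | −0.32 | 0.00 |
| observed rise | 6 | 20% | −1.12 | −0.66 | 0.00 |
| true slope | 4 | 10% | −0.40 | −0.30 | −0.22 |
| true slope | 4 | 20% | −0.81 | −0.62 | −0.46 |
| true slope | 6 | 10% | −0.61 | −0.46 | −0.26 |
| true slope | 6 | 20% | −1.25 | −0.95 | −0.56 |

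When loss follows the observed rise, the random-intercept model removes from 1 − 0.66/1.12 = 41% to 1 − 0.16/0.34 = 53% of the observed-case bias. When loss follows the true slope it removes about a quarter (1 − 0.30/0.40 = 25%). It assumes that any two visits are equally correlated, which does not hold when slopes differ between boys.

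**Step 4: scale against sampling error.** Under the same assumptions the SD of the Week 48 change is √(4² + 2 × 2²) = 4.90 or √(6² + 2 × 2²) = 6.63. With 20% of 40 boys lost (n = 32, t = 2.04) the 95% half-width is 1.77 or 2.39 points, so 0.73 and 1.12 are 41% and 47% of it. With 10% lost (n = 36, t = 2.03) the half-width is 1.66 or 2.24, so 0.34 and 0.54 are 20% and 24% of it.

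**The case against.** A reader might infer that the primary parameters have only an observed-case analysis. They do not: all four also go into a mixed model to which boys with partial data contribute, and it yields the Week 48 point estimate by simple addition. Nor is the biopsy analysis wholly different in kind, since it too pairs an observed-case summary with a mixed model. This stands. What is missing is narrower: the Week 36 and Week 48 contrasts, a covariance suited to differing slopes, and a stated missing-data assumption.

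A reader might also infer that the Week 48 rise is understated. The documents do not support that. Nothing in them says that boys who leave progress faster, and Step 1 shows that the sign can reverse.

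Loss of scans is also limited by design:
- Boys off treatment keep attending where possible (Protocol 10.2.1), and MRI follow-up continues after a liver stop (Protocol 4.2.2).
- Off-treatment data are analysed (SAP 5.1).
- A termination scan is planned unless one was done in the last 6 weeks (SAP 5.3.1).
- Missing values are counted by visit (SAP 9.1).

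The simulation includes none of these, so it may overstate the loss. The safeguards are not complete either. A termination scan before Day 308 does not fill Week 48. Scans on Days 197–223 or 281–307 fall between windows; SAP 5.1 says both that such scans are reviewed case by case and that they are only listed.

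Finally, the study is exploratory and unpowered, and Protocol 12.1.4 makes comparison with historical controls conditional. That limits the consequence, but the absolute change is still the result a single-arm study reports.

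**Conclusion.** The concern holds in a limited form. In SAP 9.7.1 the only Week 36 and Week 48 change from baseline with a stated 95% CI for the four primary MRS parameters is an observed-case mean. It can be biased if loss of scans relates to progression, and it would understate the fat-fraction rise if faster progressors leave. The planned random-intercept model corrects only part of such bias when boys' slopes differ.

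Under the stated assumptions, with loss driven by the observed rise, the observed-case bias of 0.34 to 1.12 points is about 7% to 22% of the assumed 5-point rise (0.34/5 and 1.12/5). The planned model leaves 0.16 to 0.66 points. These sizes are illustrative, and with loss unrelated to progression all three methods are unbiased.

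It would also be too strong to say that an unstructured model removes the problem. That holds only when loss depends on observed values; with loss on the true slope it still left 0.22 to 0.56 points. The case for change is that a better estimate of the primary endpoint is available cheaply, by an approach that this SAP already accepts for biopsy data.

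**What to change.** In SAP 9.7.1, for the four primary MRS parameters:
- Estimate Week 12, 24, 36 and 48 minus Baseline, with 95% CIs, from a repeated-measures mixed model with visit fixed and unstructured covariance over the main-phase visits.
- Name a simpler fallback in advance, such as a random intercept and slope, in case the model does not converge.
- State the missing-at-random assumption, as SAP 9.7.3 does.
- Use these estimates in the mean-change plot for the main-phase visits, and keep the observed-case table as supportive.

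The cost is SAP wording and some programming. It is more than extra contrasts, because the covariance of the planned model changes: five visits need 5 × 6/2 = 15 covariance parameters from about 40 boys, which is why the fallback is needed. The change gives no protection if loss depends on unobserved progression, and the report should say so.

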9.7.2 Cardiac MRI (Cohort 3)

All analyses will be performed using the Cardiac MRI population.

Details concerning the analyses of the cardiac MRI parameters will be added in a later version of the SAP.

9.7.3 Fibre Regeneration (via Biopsy) (Cohorts 1 and 2)

All analyses will be performed on the Biopsy population.

Tabulations will be over all subjects and will not provide separate information for the different cohorts.

Imputation will not be used for missing data with summaries and plots, and so subjects with missing baseline or Week 24/48 data will be excluded from presentations for the relevant time-point and change from baseline presentations. However, mixed effect models will be used to make comparisons to baseline; these analyses will use all available data and adjusts the results for missing data under the assumption of missing at random.

Summary tables will acknowledge the number of subjects who have their biopsy performed at Week 24 and Week 48 (e.g. if a subject isn't supposed to have a Week 24 measurement it will not be counted as missing).

The total number of fibres assessed with each assay will be summarized using descriptive statistics (n, median, Q1, Q3, minimum and maximum) by visit. These variables won't be included in any other analyses.

The percentage of fibres (%fibre) with 0, 1, 2 and 3 MHCd/Utrphin intensity will be excluded from analyses unless specifically mentioned.

For each assay (Myosin and Utrophin) the number of subjects contributing 1 or 2 samples worth of data will be tabulated for each visit for each of the two groups (Week 24 and Week 48). Where there is 1 sample with data the number of subjects with 1, 2 and 3 sections will be tabulated and where there are 2 samples with data the number of subjects with 2, 3, 4, 5 and 6 sections will be tabulated.

9.7.3.1 Developmental Heavy Chain Myosin (MHCd), Utrophin Expression and Fibre Diameter

Absolute values and changes from baseline in parameters (including % fibre parameters) will be summarized for the Week 24 and Week 48 visits separately.

The change in parameters at Week 24 and Week 48 will also be estimated using a mixed effects model that acknowledges the random effects of subject, samples within subjects and sections for each sample. Visit (Baseline and the relevant Week) will be fitted as a fixed effect and the change from baseline estimated along with its 95% confidence interval. Week 24 and Week 48 data will be analyzed separately.

The mean percentage of fibres with intensity scores of 1, 2 and 3 (i.e. excluding 0), for Myosin and Utrophin, will be plotted as stacked bar charts by visit – with the baselines for the two groups (Week 24 or Week 48) presented separately.

%MHCd, Fibre Diameter (mean), Utrophin Intensity (mean) and Utrophin Heterogeneity Score

The following plots will be presented for %MHCd, fibre diameter (mean), Utrophin intensity (mean) and Utrophin heterogeneity score.

Individual subject data will be plotted against visit as individual line plots (spaghetti plots).

Week 24 and Week 48 changes from baseline will also be plotted against age on Day 1 and baseline, using different symbols to identify the Week. The Pearson correlation coefficient (for each week) will be footnoted on the plots.

Plots will also be produced for each subject against visit showing each section result within each sample. The sample will be identifiable by the symbol used.

Waterfall plots will be presented for Week 48 changes from baseline and box and whisker plots will display the Baseline, Week 24 and Week 48 data. As subjects only have data collected at either Week 24 or Week 48 the baseline data will be presented separately for these two groups.

Mean changes from baseline, with associated 95% confidence intervals, will be plotted against visit.

9.7.3.2 % Necrosis/Inflammation, % Regeneration, % Fat and % Collagen

Absolute values and changes from baseline in each parameter will be summarized for the Week 24 and Week 48 visits separately.

The change in each parameter will also be estimated using a mixed effects model, fitting a fixed effect for visit (Baseline and the relevant Week) and random effects for subject and sample within subjects for each visit. The change from baseline will be estimated along with its 95% confidence interval.

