5.3.3.1 Developmental Heavy Chain Myosin (MHCd), Utrophin Expression and Fibre Diameter

Each sample will have, where possible, 3 sections assessed – different sections will be used for the Myosin and Utrophin assays. For each of these sections the following will be determined from the Myosin assay:

- Percentage of MHCd positive fibres (%MHCd positive)
- Percentage of fibres with 0, 1, 2 and 3 MHCd intensity
- MHCd heterogeneity score
- Fibre diameter - mean
- Fibre diameter – standard deviation

For the other sections the following will be determined from the Utrophin assay:

- Utrophin intensity – mean
- Utrophin intensity – standard deviation
- Utrophin intensity – mean, where utrophin expression is $\geq 75\%$ around the fibre
- Utrophin intensity – standard deviation, where utrophin expression is $\geq 75\%$ around the fibre
- Percentage of fibres with 0, 1, 2 and 3 Utrophin intensity
- Utrophin heterogeneity score

In addition to these parameters the percentage of Utrophin positive fibres (%UT positive) will be derived as (100 - % of fibres with 0 intensity).

The total number of fibres will also be recorded for both assays, but this is only information concerning the assay and isn't to assess treatment effect.

If there was a technical issue with the assay a value may be excluded from analyses. This exclusion has to be justified and documented by the pathologist/technician following their assessment of the stained image.

For each subject at each time-point the average will be calculated across sections for each sample and then the average will be calculated from the two sample averages. Changes from baseline will then be calculated from these averages.

5.3.3.2 % Necrosis/Inflammation, % Regeneration, %Fat and %Collagen

For each biopsy sample the % of necrosis / inflammation, % regeneration, %fat and %collagen will be estimated by semi-quantitative pathology assessment. Note that a single section stained with haematoxylin and eosin (H&E) will be taken from each sample to calculate % of necrosis / inflammation, % regeneration and %fat. A second section from each sample is stained with Masson's trichrome (MT) to calculate collagen.

Values from the two samples will be averaged. Changes from baseline will then be calculated for these averages.

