9.10 Relationship Analyses (Cohorts 1 and 2)

9.10.1 Relationship with SMT C1100 and Metabolite Exposures

The following Week 12, 24, 36 and 48 data will be plotted against SMT C1100 concentrations:

- MRI parameter changes from baseline (MRS fat fractions for the Vastus Lateralis and Soleus, and MRS T2 for Vastus Lateralis and Soleus)
- %MHCd change from baseline * (Weeks 24 and 48 only)

- Fibre diameter (mean) change from baseline * (Weeks 24 and 48 only)
- Utrophin intensity (mean) change from baseline * (Weeks 24 and 48 only)
- Utrophin heterogeneity score change from baseline * (Weeks 24 and 48 only)
- 6MWD change from baseline
- NSAA (total) change from baseline
- 10 metre walk/run duration change from baseline
- Time to stand change from baseline
- PUL total score change from baseline
- PODCI global function scale change from baseline

* based on average values across samples/sections ([Section 5.3.2](#)).

For a visit, the above response will be plotted separately with relevant observed Week 12 C_{trough} and the simulated parameters C_{max} and C_{av} .

The Pearson correlation coefficients (for each week) will also be presented in the footnote of the plots.

These plots will also be produced for the metabolites DHDI and DHDIII.

Any other exposure response modeling conducted will be reported separately.

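### The biopsy mixed model in SAP 9.7.3.1 has no subject-by-visit random effect, so its 95% CI for mean change is too narrow whenever boys differ in true change

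*SAP*

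**What the plan says.** SAP 9.7.3.1 describes a "mixed effects model that acknowledges the random effects of subject, samples within subjects and sections for each sample". Visit (baseline and the relevant week) is the fixed effect, and Week 24 and Week 48 are modelled separately. No covariance structure, code or degrees-of-freedom method is given.

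SAP 9.7.3.2, for necrosis/inflammation, regeneration, fat and collagen, instead has "random effects for subject and sample within subjects for each visit". Here SAP 5.3.3.2 says that "a single section stained with haematoxylin and eosin (H&E) will be taken from each sample", with a second section for the collagen stain, so each parameter has one reading per sample.

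The sampling scheme is in SAP 5.3.3 and 5.3.3.1: two samples at each time-point and, for the myosin and utrophin assays, up to three sections per sample. For per-boy values, "the average will be calculated across sections for each sample and then the average will be calculated from the two sample averages".

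SAP 9.7.3 says of the mixed models that "these analyses will use all available data and adjusts the results for missing data under the assumption of missing at random". It pools the formulations: "Tabulations will be over all subjects and will not provide separate information for the different cohorts". For four parameters, 9.7.3.1 also promises a plot: "Mean changes from baseline, with associated 95% confidence intervals, will be plotted against visit". How those plotted intervals are calculated is not stated.

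**The concern.** A random subject effect lets boys differ in level. It does not let them differ in change, nor let a whole biopsy shift at one visit relative to the other. That variation is the subject-by-visit variance, Vsv. Without a term for it, the model treats the four samples from a boy as if, visit mean aside, they differed only by sample and section noise. It then judges the mean change against an error that is too small and has too many degrees of freedom.

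The plan itself gives reason to expect Vsv above zero. Formulations F3 and F6 are pooled, although Protocol 8.2 reports maximum plasma levels more than six-fold higher with F6. Protocol 1.1 describes high between-patient variability in exposure on F3. SAP 9.10.1 plots exposure against these same changes, for example "Utrophin intensity (mean) change from baseline * (Weeks 24 and 48 only".

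Changes in utrophin and in regeneration markers are secondary endpoints, and utrophin modulation is the proof-of-concept question. With no hypothesis test planned, readers will judge certainty from the interval width. If the plotted intervals rest on per-boy averages, the report could show two different 95% intervals for the same change.

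**Working it through.** The plan states no interval width, power or variance component for these endpoints, so there is no figure to reproduce. The check is algebra on the planned layout, followed by simulation.

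**Inputs.** Protocol 4.1.1 puts the first 8 boys of Cohort 1 at Week 24 and alternates the other 22 (11 and 11). It splits Cohort 2 as 6 and 4. Week 24: 8 + 11 + 6 = 25. Week 48: 11 + 4 = 15. Each boy has 2 visits × 2 samples × 3 sections. Vsample, Vsection and Vsv are not given and are varied.

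**Nested reading (samples distinct at each visit).** Write Vm = Vsample + Vsection/3 for the variance of a sample mean and r = Vsv/Vm.

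- A boy's change is a difference of two two-sample means, with variance 2Vsv + 2(Vm/2) = Vm + 2Vsv. The correct variance of the mean change is (Vm + 2Vsv)/n, on n − 1 df.
- The listed model pools the boy-level change stratum (n − 1 df, expectation Vm + 2Vsv) with the sample-within-visit stratum (2n df, expectation Vm). Its error mean square has expectation [(n − 1)(Vm + 2Vsv) + 2n·Vm]/(3n − 1), close to Vm + (2/3)Vsv, on 3n − 1 df.
- Example, n = 25, r = 1, Vm = 1: (24 × 3 + 50 × 1)/74 = 1.65, against a correct value of 3. The SE ratio is √(1.65/3) = 0.74.

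Coverage of the nominal 95% interval, by simulation:

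| r | Model SE / true SE (n = 25) | Coverage, n = 25 or 15 | Coverage with the term |
|---|---|---|---|
| 0 | 1.00 | 95% | 95% |
| 0.1 | 0.94 | 94% | 95% |
| 0.25 | 0.88 | 92% | 95% |
| 0.5 | 0.81 | 89% | 95% |
| 1 | 0.74 | 85% | 95% |
| 2 | 0.68 | 81–82% | 95% |
| 4 | 0.63 | 78% | 95% |

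Sections remain clustered within sample in this model, so the whole fault is the missing term, and it vanishes at r = 0.

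**Shared-label reading (samples numbered 1 and 2, with the same effect carried across visits).** The text does not exclude this coding. The error then pools subject-by-visit (n − 1 df), sample-by-visit (n df) and section (8n df). Coverage falls short even at Vsv = 0: about 64%, 78%, 84% and 92% when section variance is 0.1, 1, 2 and 10 times sample variance. With the two variances equal, it is about 73%, 64% and 53% at Vsv = 0.25, 1 and 4 times sample variance.

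**Missing second biopsies.** REML with one value per sample, n = 25 and 3 boys with baseline only, gives coverage of about 89%, 82% and 78% without the term at Vsv = 0.25, 1 and 4. With the term it is 94%, 95% and 94%. These rest on 400 trials per setting, so they carry 1 to 2 points of Monte Carlo error. They are in line with the complete-data figures.

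**The case against.** The strongest reply is that 9.7.3.1 is prose, not a model statement. It says the model acknowledges certain effects, and the program may already contain the missing one. That is possible, but the term is not in the SAP, and stating it would then cost nothing.

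Second, the table assumes that every boy gives two usable samples at each visit, whereas SAP 9.7.3 expects some to give one. For a boy with one sample per visit, a visit-specific sample effect already does the work of the subject-by-visit effect. This stands, and it reduces the size. With about half the boys giving one sample, coverage at r = 1 is about 89% (n = 25) or 88% (n = 15) rather than 85%, and at r = 0.25 about 93%. If every boy gave one sample, it would be about 95%. The tabulated values are therefore the complete-data case.

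Third, variable exposure is not variable biopsy response, and the protocol says the plasma level needed to activate the utrophin promoter is unknown. This also stands: it makes Vsv above zero plausible but does not fix r. At r between 0.1 and 0.25 the loss is only 1 to 3 points. The very low coverages belong to the shared-label coding, which the plan nowhere states.

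Fourth, summaries and plots drop boys with missing data while the model keeps them, so some disagreement between outputs is expected. That does not explain a difference in width when data are complete.

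Finally, the study is unpowered, per-boy changes are also summarised and plotted, and the missing term does not itself bias the estimated mean change. These points limit the consequence, not the error.

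**Conclusion.** The concern holds. Fitted as written, the 9.7.3.1 model gives a 95% interval for mean change that is too narrow on average whenever boys differ in true change. If samples are coded as distinct at each visit, the interval is correct only when they do not differ. The size depends on variance components that the documents do not give: coverage is about 92% at r = 0.25, 85% at r = 1 and 78% at r = 4 with complete data, and closer to 95% if many boys yield one sample per visit.

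Section 9.7.3.2 is ambiguous rather than wrong, because its closing phrase about visits may or may not apply to the subject effect. The plotted intervals for the four parameters are unaffected if they are built on per-boy averages. For parameters without such a plot, the model interval is the only one specified. No formal decision depends on this, but it should be corrected because these intervals convey how well the mean biopsy change is known.

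**What to change.** In both 9.7.3.1 and 9.7.3.2, state the random effects as subject, subject-by-visit, and sample nested within subject-by-visit. Section is the residual in 9.7.3.1. Sample is the residual in 9.7.3.2, where each stain has one section per sample. Name a small-sample degrees-of-freedom method such as Kenward-Roger, and report the estimated variance components.

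Keep the mixed model, so that boys with a single biopsy still contribute under missing at random. Add a paired analysis of the per-boy averages as a check; it is not equivalent when biopsies are missing. State how the plotted mean-change intervals are calculated, so that the two sets can be reconciled.

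The cost is one sentence in each section and one extra variance component, estimable because boys give two samples per visit (less precisely if many give one). If Vsv is zero, intervals widen on average by about 3% (n = 25) to 5% (n = 15). At r = 1 they widen by about 39% to 43%, which is the width needed for 95% coverage.
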